1.2.2. TRIAL TIMELINE

Site opening	: August 2015
First Visit First Subject (group 1)	: September 2015
First randomization (group 1)	: September 2015
First Visit First Subject (group 2)	: October 2015
First randomization (group 2)	: November 2015
First Visit First Subject (group 3)	: January 2016
First randomization (group 3)	: January 2016
First Visit First Subject (group 4)	: March 2016
First vaccination (group 4)	: March 2016
First Visit Last Subject	: February 2016
Last Visit Last Subject	: February 2017
Antibody assays	: August 2015 – April 2017
Exploratory laboratory assays	: April 2016 – December 2017
Final statistical analysis	: October 2016 – June 2017
Clinical study report	: February 2017 and then August 2017

1.3. SAMPLE SIZE

Acknowledging that due to the small sample size, the power of Phase I trials is in general very low, and that only frequent events can be detected with sufficient power, 12 volunteers receiving active vaccination per dose level in groups 1, 2 and 3 constitute a trade-off between detectable event rate and power in the context of a phase I trial (Buoen, J Clin Pharmacol 2003). A sample size of 12 volunteers allows for observing at least one primary safety endpoint event with 80% power if the underlying event rate is at least 12.6%.

If no primary safety endpoint event is observed among 12 volunteers, the upper bound of a two-sided 95% confidence interval for the event rate would be 26%.

If no primary safety endpoint event is observed among 36 volunteers (pooled across groups 1, 2, 3), then the upper bound of the 95% confidence interval for the event rate would be 10%.

1.4. RANDOMIZATION AND BLINDING

Vaccine and placebo will come in identical, coded vials.

The vials will be coded with group number and vial number: group1: 101 – 116, group 2: 217 – 232, group 3: 333 – 348 and group 4: 449 – 454, for the respective groups described above under point VI.2 “General study plan and design” of the protocol.

To ensure randomized allocation, the vials must be used by the site in their consecutive order of vial numbers within a given dose group. The vial number given to the volunteer (and the time of administration) will be recorded both in the CRF and the medical record (source data).

Vaccine and placebo are not distinguishable when frozen, allowing for allocation concealment, and are not distinguishable at the 10^7 dose level when thawed. For higher dose levels (10^8 , 10^9), where vaccine and placebo may be distinguishable when thawed, observer-blinding will be established, by the fact that the vaccine will be prepared and administered by a study nurse not involved in any other trial procedures.

The randomization list, establishing the order of vials and the correspondence between vial number and active vaccine or placebo group will be generated centrally by the statistician at the EUCLID clinical trials platform prior to the start of the study and kept confidentially in a secure environment.

The list with the codes/information if a vial contains vaccine or placebo will only be available at the statistics center (EUCLID), Lund University Hospital pharmacy (for emergency unblinding), at the manufacturer’s site (Q Biological; for labelling the vials) and at the sponsor pharmacovigilance site. The decision whether the code shall be broken for an individual volunteer or all participants will be made by the investigator.

For purposes of interim analyses, the statistician responsible for the analysis will maintain the codes in strict confidence with no communication of any individual codes until final data lock.

An identical series of back up vials will be generated for each group. These vials will be kept and stored at the manufacturer’s site.

Since access to results of the cultivation of BPZE1 from the nasopharynx samples and the antibody determination may lead to treatment unblinding, these results will be strictly controlled within the respective laboratory. The access of these results outside the laboratory will be contingent on having a previous access to the randomization list and therefore will only be authorized after the completion of the study, with the exception a statistician in order to perform an interim analysis after 28-days follow-up. At the end of the trial, the study will be unblinded after all safety and laboratory results from 6 months follow up are monitored and the data bases are locked. The volunteers will be blinded until after the 12 month-follow up.

Unblinded interim reports for the DSMB will be prepared before escalation to the next dose by the trial statistician. An additional interim analysis will be performed when culture results are available from twenty-eight days after vaccination of the high dose group 3 and 4, respectively. For the latter, another statistician will get access to the randomization list for groups 1-3 to provide a summary of safety and colonization data to the Sponsor/ILiAD for use in discussion with regulatory agencies about a Phase II study. The interim analysis will provide no information about individual volunteers that could reveal the vial codes and the statistician performing the interim analysis will not be involved in any other trial procedure or in the final statistical analyses.

A clinical study report containing data of the primary and secondary end-points will be prepared when the safety and laboratory results from 6 months follow up are monitored and the data bases are locked. A separate report will be prepared containing the results of the 12 months follow up.

2. STATISTICAL ASPECTS

Final statistical analyses and interim reporting to the DSMB will be performed by the EUCLID Clinical Trials Platform. Confidential statistical analysis for the FDA during the ongoing trial, including safety and colonization data up to Day 28 in groups 1, 2 and 3, will be performed by a statistician outside of EUCLID, designated by Iliad.

2.1. ANALYTICAL STRATEGIES AND STUDY POPULATIONS

Exclusion from the analysis can be considered for those participants who meet, in particular, one of the following conditions:

- participants who never exposed to the trial intervention (provided they do not have knowledge of the group to which they were randomized);
- participants who withdrew their consent;
- participants who were wrongly enrolled due to major eligibility criterion(a) not being met

The decision to exclude a participant from the analysis is taken by the Executive Committee after documentation by the Clinical Trials Unit, blinded to study intervention and to the participants' evolution after enrolment.

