If no primary safety endpoint event is observed among 36 volunteers (pooled across groups 1,2,3), then the upper bound of the 95% confidence interval for the event rate would be 10%.

XV.2. STATISTICAL METHODS

XV.2.1. Analysis strategy

Statistical analyses will be performed by the EUCLID Clinical Trials Platform (except for the interim analysis of the colonization and safety data when culture results are available from twenty-eight days after vaccination of the high dose group 3, mentioned below).

All participants having received at least one injection will be included in the analysis. All primary analyses will be performed per dose group and randomized allocation (for arms receiving active vaccination) and for the pooled placebo arms (unless there is evidence for a time trend in placebo observations between group).

The main analysis of the primary endpoint is conducted:

- By modified intention to treat: This means that all randomized participants who received a vaccine dose are included in the analysis in the group and intervention arm to which they were initially randomized and all their data is used regardless of protocol deviations during the trial/study.
- In this analysis, participants with missing follow-up data will be assumed to be event-free, unless the site has any knowledge of a safety event having occurred and has notified this in the e-CRF.

No statistical comparisons between dose groups or randomized allocations will be performed but two-sided 95% confidence intervals will be displayed..

Intra-group statistical comparisons will be performed for immunogenicity markers.

In ancillary analyses, appropriate statistical models for the analysis of longitudinal data may be used to estimate the slopes of changes in immunogenicity markers per group. Methods for high-dimensional data may be used to assess the interrelationships between different immunogenicity markers.

Quantitative variables

Quantitative variables will be described in terms of absolute frequency, median, interquartile range, minimum, and maximum.

Intra-group comparisons will be made using paired Student t-test or Wilcoxon paired signed-ranks test according to the distribution of variable of interest for analyzing change from baseline to post-vaccination within a given dose group or randomized allocation. Transformations to normalize the variables can be made if necessary.

Qualitative variables

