2.1.1. PRIMARY SAFETY ENDPOINT

- **Definition**

The primary safety endpoint will be the number and proportion of participants, per dose group and randomized allocation, with at least one of the following adverse events between Day 0 (Visit 2) and Day 28 (Visit 8):

- Cough and spasmodic cough of grade 2 or higher.
- Other respiratory tract AE related or possibly related to vaccination of grade 3 or higher.
- Any other AE related or possibly related to vaccination of grade 3 or higher.

- **Strategy for the main analysis**

The main analysis is conducted:

- By modified intention to treat: This means that all randomized participants who received a vaccine dose are included in the analysis in the group to which they were initially randomized and all their data is used regardless of protocol deviations during the trial/study.
- In this analysis, participants with missing follow-up data will be assumed to be event-free, unless the site has any knowledge of a safety event having occurred and has notified this in the e-CRF.

- **Strategy for secondary analyses**

- With the strategy of *definitely missing follow-up data (i.e. premature termination of follow-up) = failure*.
(For non-compliant participant, it will be assumed that no safety event occurred during the missing visits)

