3.1.2. MAJOR PROTOCOL DEVIATIONS

The other following deviations are described per category:

- Randomized participants who did not receive the trial intervention
- Participants who received the wrong intervention or incorrect dose
- Participants who received a forbidden concomitant intervention. The following therapies should be avoided during the first month after vaccination:
 - Antibacterial agents effective against *B pertussis*.
 - Immunoglobulin, corticosteroids for systemic use or for use in the respiratory tract (e.g. nasal steroids, inhaled steroids), other immunosuppressive agents or immunostimulating agents.
 - *Pertussis* vaccines.
 - Topical nasal therapies.

If it is necessary to give a medication or a vaccine, this shall be permitted for obvious reasons be permitted. All medications and vaccines will be documented in the case report form (CRF). The volunteer will be followed as pre-planned for adverse events. The immunological part of the study can also continue, but the results from the volunteer should be reported separately in the statistical analyses.

Deviations per participant are described.

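### SAP 2.1 allows vaccinated participants to be excluded for withdrawn consent or ineligibility, which contradicts the rule that everyone dosed is analysed for safety; the safety set needs one definition

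*Combined protocol and SAP*

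**What the plan says.** **Exclusions.** SAP 2.1 states: "Exclusion from the analysis can be considered for those participants who meet, in particular, one of the following conditions". Three conditions follow: never exposed to the intervention, withdrawn consent, and "participants who were wrongly enrolled due to major eligibility criterion(a) not being met". Only the first concerns people who were not dosed. The Executive Committee decides, after documentation by the Clinical Trials Unit and blinded both to intervention and to what happened to the participant after enrolment.

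**Inclusion.** Protocol XV.2.1 says: "All participants having received at least one injection will be included in the analysis". The synopsis has an equivalent sentence. SAP 2.1.1 defines the modified ITT set for the primary safety endpoint: "all randomized participants who received a vaccine dose are included in the analysis in the group to which they were initially randomized". It adds that protocol deviations do not remove any data, and protocol XV.2.1 has the same rule. SAP 2.1.2 carries this strategy over to the secondary safety endpoints.

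**Missing follow-up.** In the main analysis of SAP 2.1.1, a participant with missing follow-up counts as event-free unless the site has notified an event. A secondary analysis counts premature termination of follow-up as failure.

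**Dosing errors.** SAP 3.1.2 lists as a deviation: "Participants who received the wrong intervention or incorrect dose". No safety analysis by product or dose actually received is given.

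**Group 4.** The six open-label recipients of 10^9 cfu are not randomized. The protocol sentence on everyone dosed covers them; the mITT sentence in SAP 2.1.1, read literally, does not.

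**The concern.** SAP 2.1 makes the denominator of the primary safety rate partly discretionary, while SAP 2.1.1 fixes it. The flowchart in SAP 3.2.1 counts participants excluded from the analysis and participants in the mITT analysis as separate items, without saying how one constrains the other. Two analysts could follow the SAP and report different rates.

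The withdrawn-consent condition matters most. Protocol VIII requires follow-up of withdrawn subjects to find out whether an adverse event was the reason, so the protocol itself expects that link. Protocol XIII.2 asks for particular efforts to collect adverse events over at least 28 days after a premature discontinuation. SAP 2.1 could then discard what those sections require to be collected.

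Ineligibility is a baseline matter and less likely to depend on outcome. Even so, exclusion criterion 11 is asthma or another chronic respiratory problem. Someone wrongly enrolled on that criterion and then vaccinated is plainly relevant to a cough and respiratory endpoint.

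A lesser gap is that, under as-randomized assignment, an event after a wrong vial is tabulated under a product or dose the person did not receive.

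**Working it through.** **Inputs.** SAP 1.3 plans "12 volunteers receiving active vaccination per dose level in groups 1, 2 and 3". It gives a chance of at least one event "with 80% power if the underlying event rate is at least 12.6" per cent and, for zero events among 12, "the upper bound of a two-sided 95% confidence interval for the event rate would be 26" per cent. SAP 2.2.1 specifies exact binomial intervals. Protocol VIII says withdrawn subjects are not replaced, so an exclusion shrinks the arm. The documents give no number of exclusions; one among 12 is an assumption used throughout.

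**Formulas.** Chance of at least one event: 1 − (1 − p)^n. Upper two-sided 95% bound with zero events: 1 − 0.025^(1/n). With events, Clopper-Pearson limits.

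**Reproducing the plan.**
- 1 − 0.874^12 = 80.1%, in line with the stated 80%.
- 1 − 0.025^(1/12) = 26.46%, stated as 26%.
- 1 − 0.025^(1/36) = 9.7%, stated as 10%.

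**One exclusion in an arm of 12.**

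| Situation | Rate | Exact 95% CI |
|---|---|---|
| One event, nobody excluded | 1/12 = 8.3% | 0.2–38.5% |
| The participant with the event is excluded | 0/11 = 0% | upper bound 28.5% |
| A participant without an event is excluded | 1/11 = 9.1% | 0.2–41.3% |
| No events, nobody excluded | 0/12 = 0% | upper bound 26.5% |

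Pooled over Groups 1–3, dropping the only event turns 1/36 (2.8%, upper bound 14.5%) into 0/35 (upper bound 10.0%).

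At a true rate of 12.6%, the chance of seeing at least one event is 80.1% with 12, 77.3% with 11 (1 − 0.874^11) and 74.0% with 10 (1 − 0.874^10).

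**Effect on the sensitivity analysis.** Suppose one vaccinee withdraws consent before Day 28, no event is notified, and nobody else in the arm has an event.
- Participant kept: the main analysis gives 0/12 (upper bound 26.5%) and the secondary analysis gives 1/12 (8.3%, 0.2–38.5%). The gap of 8.3 percentage points shows how much the event-free assumption matters.
- Participant excluded under SAP 2.1: both analyses give 0/11 (upper bound 28.5%), and the gap disappears.

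**The case against.** The strongest reply is that SAP 2.1 is a general, permissive clause and SAP 2.1.1 the specific rule for this endpoint. The specific rule keeps all dosed randomized participants and retains site-notified events. Its early-termination analysis also presupposes that people who leave stay in the set. On that reading one cross-reference is missing, and nobody plans to drop vaccinees. The blinded decision is a further protection against choosing exclusions by result.

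Much of this stands. The specific rule is probably what was meant, and the blinding is a real safeguard. But the SAP does not say that the specific rule prevails. Blinding the committee does not break the link between a reaction and the participant's own decision to leave, and blinding to intervention is impossible in open-label Group 4.

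On dosing errors, the reply is that SAP 3.1.2 describes deviations per participant and no between-arm tests are planned, so an error would be visible. That is fair, and makes this limb a secondary addition.

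A reader might infer three stronger points, which the documents do not support:
- **A general downward bias in the safety rate.** Excluding a non-event raises the rate, and as-randomized assignment can move an event either way between arms.
- **Loss of Group 4's safety data, 6 of the 18 planned recipients of 10^9 cfu.** The protocol sentence covers everyone dosed, SAP 1.1.2 assesses six-month safety in Groups 1–4, and SAP 3.5.2 and 3.6 report by group. Leaving Group 4 out of the mITT set would not alter the rates in Groups 1–3.
- **A need to pool Groups 3 and 4.** Group 4 is open-label and selected for PRN IgG of at least 20 IU/ml, an exclusion from Groups 1–3. Protocol III.2 reports higher pre-vaccination PRN antibody in culture-negative high-dose subjects. The synopsis gives Group 4 an exploratory aim, and SAP 1.3 pools only Groups 1–3.

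**Conclusion.** The contradiction is real and bears on the primary endpoint: SAP 2.1 permits an exclusion of dosed participants that protocol XV.2.1 and SAP 2.1.1 rule out. With 12 vaccinees per arm, a single exclusion can remove the only event or raise the observed rate. These sizes are illustrations resting on one assumed exclusion; the fall to 0/11 further assumes that the excluded person had the arm's only event. What the documents establish is an unsettled denominator. They do not establish a bias of known direction or a plan to discard data. The missing as-received analysis and the word randomized in SAP 2.1.1 are smaller gaps that the same edit can close.

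**What to change.** 1. In SAP 2.1, state that for the primary and secondary safety analyses the exclusions apply only to participants who were never dosed. For withdrawn consent, use data up to withdrawal where the consent terms allow.
2. Define a safety set of everyone dosed, analysed by product and dose actually received. Keep the as-randomized mITT analysis alongside it.
3. State that Group 4 belongs to the safety set and is reported as its own group, so that the word randomized in SAP 2.1.1 no longer leaves its coverage open.
4. In the SAP 3.2.1 flowchart, show the safety set and the mITT set, with the reason for any difference.

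The cost is SAP wording, plus one extra set of tables if dosing errors occur. No additional data collection is needed. The wording should be settled before any participant is considered for exclusion.

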2.1.1. PRIMARY SAFETY ENDPOINT

- **Definition**

The primary safety endpoint will be the number and proportion of participants, per dose group and randomized allocation, with at least one of the following adverse events between Day 0 (Visit 2) and Day 28 (Visit 8):

- Cough and spasmodic cough of grade 2 or higher.
- Other respiratory tract AE related or possibly related to vaccination of grade 3 or higher.
- Any other AE related or possibly related to vaccination of grade 3 or higher.

- **Strategy for the main analysis**

The main analysis is conducted:

- By modified intention to treat: This means that all randomized participants who received a vaccine dose are included in the analysis in the group to which they were initially randomized and all their data is used regardless of protocol deviations during the trial/study.
- In this analysis, participants with missing follow-up data will be assumed to be event-free, unless the site has any knowledge of a safety event having occurred and has notified this in the e-CRF.

- **Strategy for secondary analyses**

- With the strategy of *definitely missing follow-up data (i.e. premature termination of follow-up) = failure*.
(For non-compliant participant, it will be assumed that no safety event occurred during the missing visits)

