Subjects may be withdrawn from the study and/or the study vaccination schedule for the following reasons:

- At their own request
- On PI decision
- The DSMB, PI and the sponsor have the right to terminate the study at any time if adverse events which may be related to the study vaccine occur.

In all cases, the reason for withdrawal can if available be recorded in the CRF. The subject must be followed up to establish whether the reason was an adverse event, and, if so, this must be reported in accordance with the procedures in Section XIII. *"Recording and reporting of Adverse Events following immunization"*. The adverse event should be followed-up by the investigator until its complete resolution or stabilization.

As far as possible, as many examinations as possible scheduled during follow-up and in particular for the final study day (at 6±1 months) must be performed on all subjects who received the investigational product (including withdrawn subjects) but did not complete the study according to protocol.

The investigator must make every effort to contact subjects lost to follow-up. This information will be documented in the CRF. Withdrawn subjects will not be replaced.

IX. Follow up of volunteers

After successful completion and evaluation of the present study the volunteers may be asked if they would like to participate in a follow up study after due approval from the Medical Product Agency and the Local Ethics Committee.

X. Investigational Medicinal Products i.e. Study vaccine

X.1. IDENTITY OF STUDY VACCINE

Live attenuated *Bordetella pertussis* BPZE1 bacteria or placebo.

X.2. SUPPLY OF STUDY VACCINE

Formulated attenuated *Bordetella pertussis* BPZE1 at 3 different doses (Colony Forming Unit) (see Investigational Medicinal Product (IMP) Dossier).

Liquid formulation of live attenuated *Bordetella pertussis* BPZE1 bacteria in phosphate buffered saline (containing sodium chloride and potassium chloride) and 5% saccharose at three different colony-forming units (see IMP Dossier).

X.3. DOSES AND TREATMENT REGIMENS

A dose escalation placebo controlled study will be performed, starting with a low dose (10^7 cfu), followed by a medium dose (10^8 cfu), followed by a high dose (10^9 cfu) + placebo consisting of the formulation buffer (phosphate buffered saline (containing sodium chloride and potassium chloride) and 5% saccharose).

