Qualitative variables will be described in terms of number, proportion and exact binomial confidence interval of proportion.

Intra-group comparisons will be made using McNemar test or other, depending on the number of modalities of the variables of interest.

Titers

Geometric means and their 95% confidence interval will be calculated for titers.

XV.2.2 Analysis software

Analyses will be performed using SAS® software (version 9.3 or higher) and R software.

XV.2.3 Analysis plan

A detailed statistical analysis plan will be established before the first statistical analyses of the trial.

Descriptive statistics will be provided for demographic and other baseline characteristics.

Hematology

Pre- and post-vaccination values of cell blood counts (haemoglobin, total and differential WBC, RBC and platelets) will be described for each group separately. Within group comparisons may be done using appropriate tests for paired measurements.

Primary Safety endpoint

The primary endpoint will be described per group and randomized allocation, in modified ITT population, with participants with missing follow-up data considered event-free in primary analysis. Numbers, percentages and 95% confidence intervals will be shown. Each individual component of the primary endpoint will also be described.

Secondary endpoints

Secondary endpoints will be described per group and randomized allocation, displaying numbers, percentages and 95% confidence intervals (qualitative variables); medians and interquartile intervals (quantitative variables) or geometric mean and 95% confidence interval (antibody titers).

Number, time of occurrence and duration of secondary safety endpoints will be described.

Colonization endpoints will be described (number and proportion of participants with colonization at each post-vaccination visit; number of visits during which bacteria are detected; magnitude of bacterial colonization (number of cfu) per post-vaccination visit)

Pre- and post- vaccination serum IgG and IgA antibody endpoints will be described per group and randomized allocation. Within group comparisons may be done using appropriate tests for paired measurements.

Cough, spasmodic cough and any symptom from the respiratory tract, as well as antibody titers, will be described for each of the vaccine groups and the pooled placebo group, and for the groups of colonized and non-colonized individuals.

Exploratory endpoints

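### A continuing participant with unrecovered Day 0–28 data counts as event-free in both the main and the sensitivity analysis of the primary safety endpoint, so no planned analysis bounds that risk

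*Combined protocol and SAP*

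**What the plan says.** Main rule. SAP 2.1.1 analyses every randomised participant who received a dose, and "participants with missing follow-up data will be assumed to be event-free, unless the site has any knowledge of a safety event having occurred"; the site must also have notified that event in the e-CRF. Protocol XV.2.1 has the same rule. Protocol XV.2.3 and the synopsis repeat it without the exception: "with participants with missing follow-up data considered event-free in primary analysis".

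Sensitivity rule. SAP 2.1.1 adds one secondary strategy, in which follow-up that is definitely missing because it ended prematurely counts as failure. For a non-compliant participant, however, "it will be assumed that no safety event occurred during the missing visits". SAP 2.1.2 applies the same strategies to the secondary safety endpoints.

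Planning figures. SAP 1.3 and Protocol XV.1 rest on "12 volunteers receiving active vaccination per dose level in groups 1, 2 and 3". They give the chance of at least one event "with 80% power if the underlying event rate is at least 12.6"%. For no events among 12, "the upper bound of a two-sided 95% confidence interval for the event rate would be 26"%. For no events among the 36 pooled, "then the upper bound of the 95% confidence interval for the event rate would be 10"%. Neither section mentions missing data. Protocol VIII adds: "Withdrawn subjects will not be replaced".

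**The concern.** Safety is the primary objective, and the endpoint depends largely on cough and other symptoms that volunteers record daily. The main rule keeps an unobserved person in the denominator and scores that person as observed and safe. The count can then be equal to or below the count that complete data would give, never above it. The exact interval is also computed as if all 12 had been observed.

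A sensitivity analysis in the opposite direction would normally contain this. Here it does so only for people who leave the study. Someone who stays in but whose Day 0–28 information is never recovered, for example after missing Visit 8 when the diary is handed in, is a non-event under both strategies. With 12 active recipients per dose and no replacement, one such person is a twelfth of the group.

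**Working it through.** **1. The plan's own figures.** With 0 events in n, the two-sided 95% Clopper-Pearson upper limit is 1 − 0.025^(1/n). SAP 2.2.1 and Protocol XV.2.1 specify exact binomial intervals.
- n = 12: 1 − 0.025^(1/12) = 26.46% (stated 26%).
- n = 36: 1 − 0.025^(1/36) = 9.74% (stated 10%).
- Chance of at least one event at a 12.6% rate: 1 − (1 − 0.126)^12 = 80.1% (stated 80%).

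All three reproduce, each with everyone observed.

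**2. How the two rules treat each type of participant (SAP 2.1.1).**

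| Participant with no recorded event | Main analysis | Secondary analysis |
|---|---|---|
| Complete Day 0–28 information | event-free | event-free |
| Terminated follow-up early | event-free | failure |
| Continues, missed visits, information not recovered | event-free | event-free |

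The last row is the gap. Two wording points bear on it. Missing follow-up data are not defined, and the secondary rule speaks of visits, not diary days. Premature termination is not tied to Day 28, so on the wording a withdrawal after the endpoint window could count as failure while an unobserved stretch inside the window does not.

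**3. Size.** Let m be the number of active recipients with unrecovered Day 0–28 data and no recorded event. The documents give no dropout rate; m = 1 to 3 is assumed for illustration, with no event among those observed.
- Plan: 0/n, whatever m is.
- Observed only: 0/(n − m), upper limit 1 − 0.025^(1/(n − m)).
- Missing = event: m/n, upper limit the 97.5% quantile of Beta(m + 1, n − m).

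One dose group, n = 12:

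| m | Plan, upper limit | Observed only, upper limit | Missing = event, rate | Missing = event, upper limit |
|---|---|---|---|---|
| 0 | 26.5% | 26.5% | 0% | 26.5% |
| 1 | 26.5% | 28.5% | 8.3% | 38.5% |
| 2 | 26.5% | 30.8% | 16.7% | 48.4% |
| 3 | 26.5% | 33.6% | 25.0% | 57.2% |

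Pooled active recipients, n = 36, m = 1, 2, 3: the plan gives 9.7% throughout; observed only gives 10.0%, 10.3%, 10.6%; missing = event gives 14.5%, 18.7%, 22.5%.

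**4. Chance of seeing an event.** With 12 − m observed, 1 − (1 − 0.126)^(12 − m) falls from 80.1% to 77.3%, 74.0% and 70.2% for m = 1, 2, 3.

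**The case against.** Four arguments weigh against the concern.

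- **A missed visit need not mean missing endpoint data.** The diary runs daily from Day 0 to Day 28 (Protocol XIII.2). Visits 3 to 8 each include diary review and an interview about the interval since the last visit (VI.3.4 to VI.3.9). Visit 8 has a seven-day late window. XIII.2 asks for particular effort to collect events within 28 days after early discontinuation. This stands: only information that none of these routes recovers is at issue.
- **Early terminators are already covered.** If the two unobserved people in the m = 2 row had terminated, 2/12 with upper limit 48.4% is exactly the SAP's secondary analysis. This stands. A reader might infer that the plan has no worst-case analysis; it has one, but it leaves out continuing participants.
- **Little may be missing.** Protocol III.2 reports information missing from 1 of 385 planned visits (0.26%) in the first-in-man trial, and the text appears to tie that visit to the six-month sample, outside Day 0–28. SAP 2.2.1 and 3.2.4 also report available data and observed against expected visits. This limits the expected size, but displaying missingness does not bound its effect on the endpoint.
- **The main analysis need not be replaced.** A denominator of people with an event or with complete ascertainment would keep partly observed people only when they had an event, which pushes the rate up. This stands, so the remedy is to supplement the mITT analysis.

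**Conclusion.** The concern holds in a limited form. For a continuing participant with unrecovered Day 0–28 data, both planned strategies assume no event, the error can only run toward a lower event rate and upper limit, and nothing planned bounds it. The same applies to the secondary safety endpoints.

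A reader might infer that the stated 26% and 10% bounds are wrong. The documents do not support that: these are conditional planning statements that reproduce exactly with complete follow-up. What can be too favourable is a reported result, and only if somebody is unobserved.

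In a group of 12 with no observed event, one unobserved participant separates the plan's 26.5% from 28.5% (observed only) or 38.5% (missing = event). The counts of one to three are assumed. If nobody is missing, all the analyses agree. This is a modest gap that is cheap to close, and it does not invalidate the design.

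**What to change.** Amend SAP 2.1.1, and through it 2.1.2, before unblinding:

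1. Keep the mITT main analysis, and label its event count and rate as the lower bound with respect to missing data.
2. Define missing endpoint data as Day 0–28 diary or interview information not recovered at a later contact, and report the number of such participants per arm.
3. Extend the missing = failure analysis to all of them, whether or not they terminated, and restrict it to gaps within Day 0–28 so that later withdrawal does not count.
4. Add an observed-only row with its exact interval, stating how a partly observed participant with a recorded event is handled.
5. State in SAP 1.3 that 26% and 10% assume complete follow-up.

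The cost is a few sentences and table rows, with no change to conduct or sample size. The price is a less favourable upper limit beside the main result if anyone is missing.
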